6.8 Concomitant Therapy

Any medication or vaccine (including over-the-counter or prescription medicines, recreational drugs, vitamins, and/or herbal supplements) that the participant is receiving at the time of enrollment or receives during the study must be recorded along with:

- Reason for use
- Dates of administration including start and end dates
- Dosage information including dose and frequency
- For vaccines (if applicable) include brand name and manufacturer (plus lot number if available)

Any concomitant medications may be considered on a case-by-case basis by the Investigator in consultation with the medical monitor.

6.8.1 Prohibited Medications

The following treatments/nutriments are forbidden before each pollen challenge (See [Exclusion criteria 9](#)):

- Antihistamines: within 3 days for first-generation antihistamines, within 2 days for second-generation antihistamines
- Intranasal or inhaled corticosteroids: 7 days
- Ocular, intranasal or inhaled sodium cromoglycate: 14 days
- High doses of systemic corticosteroids: 30 days
- Leukotriene antagonists: 30 days
- Intranasal or systemic decongestants: 3 days
- Tricyclic antidepressants: 7 days
- Any citrus fruits (grapefruit, orange, etc.) or their juices, as well as all fruit juices: 5 days
- Aluminum-and-magnesium containing antacids: 7 days
- Omalizumab/dupilumab: within 6 months

The following medications are prohibited during the study:

- Any antihistamine (during the washout period)
- Beta blockers
- Tricyclic antidepressants

- Monoamine oxidase inhibitors
- Vaccination with live vaccines while on study is prohibited. Administration of inactivated vaccines is allowed (eg, inactivated influenza vaccines or SARS-CoV-2 vaccines).
- Intranasal or inhaled corticosteroids
- Ocular, intranasal or inhaled sodium cromoglycate
- Systemic corticosteroids
- Leukotriene antagonists
- Intranasal or systemic decongestants
- Any consumption of citrus fruits (grapefruit, orange, etc.) or their juices, as well as all fruit juices within 5 days before and during the treatment visit.
- Any administration of aluminum-and-magnesium-containing antacids.

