2.3.1 Risk Assessment

2.3.2 Benefit Assessment

Potential benefits include contributing to the process of developing a new method of therapy as this study will contribute to the knowledge of AR management for patients and provide evidence of the benefit from pre-treatment for allergy sufferers.

All participants can expect a treatment benefit as they all will have confirmed AR diagnosis, will have demonstrated the occurrence of AR symptoms during the pollen challenge which takes place after screening, and all participants will receive at least 1 dose of fexofenadine during the study, even those in the placebo arm, which they can continue at home after the pollen challenge is over if they wish to. This study may bring a better knowledge about the benefit of pre-treatment for SAR.

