4.0 STUDY DESIGN

4.1 Overall Design

This is a Phase IIIb, randomized, double-blind, single-center, two-arm, parallel-group, placebo-controlled, proof-of-concept study, outside of Ragweed pollen season. Two Arms are planned:

- Arm A (active 2 days): two days of pre-treatment with fexofenadine, then fexofenadine 180 mg during the test pollen challenge
- Arm B (placebo 2 days): two days of pre-treatment with placebo, then fexofenadine 180 mg during the test pollen challenge

A total of 5 visits to the study site or the EEU are planned per participant.

An adequate number of participants will be screened to achieve 96 participants randomized (86 evaluable participants). Each participant will be screened, including skin prick tests at Visit 1 (V1). Eligible participants will return to the study site for a 3-hour pollen exposure (standard Ragweed pollen concentration of 3500 ± 500 grains/m³) at V2 and discharged thereafter. Only those participants with qualifying symptom scores (Total Nasal Symptom Score of 3 symptoms [TNSS-3] ≥ 4) in the last 90 minutes of the challenge will be eligible to be randomized into the study. After a washout period of at least 15 days, randomization will occur within a week, at V3 (Day 1) in a 1:1 proportion to either Arm A (active-active) or Arm B (placebo-active) group. Randomization may occur within a week after completion of the washout period, where the participants will be instructed not to take the study drug until 2 days before their planned V4. The participants will consume study drug at home, on Day 2 and Day 3. This will be followed by a Ragweed pollen challenge lasting 3 hours (standard Ragweed pollen concentration of 3500 ± 500 grains/m³) at V4 (Day 4). During this challenge, participants in both Arms will receive a single dose of fexofenadine 180 mg after pollen exposure, at Hour 3 (H3). The participants will be discharged after the challenge at V4 (Day 4). Participants will record their symptoms using a diary card (e-diary) while in the EEU and at home thereafter. On Day 5, all participants will participate in a telephonic visit, which will be recorded as End-of-Study (EOS) Visit. For return of the e-diary, the participants will come to the study site for an in-person EOS Visit. Any emergency/pandemic concerns in the future will be minimized via use of an e-diary, which is a virtual interface, to document AEs, concomitant medications, symptoms, and the treatment satisfaction questionnaire.

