4.1.3 Washout Period (≥ 15 Days)

The following information will be recorded every day preferably in the morning, via e-diary:

- Any AEs
- Concomitant medications

During the washout period of at least 15 days, any antiallergic therapy is forbidden. Please see [Section 6.8](#) for prohibited medications during the study, including the washout period.

4.1.4 Visit 3 (Randomization) Day 1

Randomization may occur within a week after completion of washout period. The following procedures will be performed on Day 1:

- Inclusion/exclusion criteria verification
- Urine pregnancy testing (for WOCBP only)
- E-diary completion
- Concomitant medication recording
- Collection of AEs
- Baseline allergic symptoms scoring
- Randomization will be performed as follows:
 - Arm A: Fexofenadine, one tablet of 180 mg in the morning for 2 days
 - Arm B: Placebo, one tablet in the morning for 2 days

4.1.5 At Home: Day 2 and Day 3 (Study Drug Intake and Diary Card Completion)

The following activities are to be completed at home in the morning on Day 2 and Day 3:

- Diary card (e-diary) completion for:
 - Allergic symptom scores, before drug intake: instantaneous assessments
 - Any AEs
 - Concomitant medications
- Study drug intake

4.1.6 Visit 4 (Test Ragweed Pollen Challenge) Day 4

The following activities are to be completed in the morning:

- Inclusion/exclusion criteria verification
- Urine pregnancy testing (for WOCBP only) before challenge
- COVID-19 testing via a rapid antigen test for SARS-CoV-2 infection before challenge
- Return study drug wallet before challenge
- Symptoms scoring before challenge
- Starting pollen challenge (hour zero [H0]): all participants will be exposed to a standard Ragweed pollen concentration of 3500 ± 500 grains/m³

If in the judgment of the Investigator, symptoms become intolerable the participants will be removed from the EEU.

- Pollen exposure will last 3 hours (H0 to H3).
 - H0 to H3: symptoms evaluation every 15 minutes
 - At H3: stop pollen exposure
 - At H3 all participants will receive one packet of fexofenadine 180 mg and will be instructed to take one tablet from the pack:
 - Arm A: single dose of fexofenadine 180 mg
 - Arm B: single dose of fexofenadine 180 mg
- H3 to H6: symptoms evaluation every 30 minutes

- At H6:
 - Physical examination
 - Vital signs
 - Nasal examination as per Investigator judgment
- Concomitant medication recording
- Participants will be questioned with regards to AEs

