4.2 Scientific Rationale for Study Design

This is a Phase IIIb, randomized, double-blind, single-center, two-arm, parallel-group, placebo-controlled, proof-of-concept study.

A double-blind, randomized, placebo-controlled design is chosen to minimize bias in data collection and interpretation. A washout period of ≥ 15 days is included between the skin prick test to identify eligible participants and randomization (D1), to prevent carry over of symptoms as well as possible drug effects from previous antihistamine therapy. The patient population to be included in this study is directly relevant to the target population for the intended therapeutic use of the study drug prior to exposure to allergen.

The results of the study will be reported in terms of the statistical significance. It will be important to bridge the gap between statistical and clinical significance to make an informed decision in recommending any intervention.¹⁶ In addition to global ratings, changes in related measures that have established consensus-based thresholds can be used to define the responder threshold for the main criteria measure. In the literature, some different thresholds for the minimum clinically important difference (MCID) have been proposed from 0.5 standard deviation (SD)¹⁷ to 1 SD¹⁸ for the improvement of the Rhinoconjunctivitis Total Symptom Score in grass-pollen-induced AR.

The study will attempt to demonstrate clinical relevance of pre-treatment in the current indication. This requires showing a robust statistical difference when comparing groups with and without pre-treatment. Therefore, the use of placebo in this study is justified and ethical.

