5.2 Exclusion Criteria

Participants are excluded from the study if any of the following criteria apply:

1. History of anaphylaxis to Ragweed pollen.
2. History of asthma or exacerbations in the past 12 months requiring regular inhaled corticosteroids for >4 weeks per year, any oral corticosteroid usage, any emergency department visit for asthma or any asthma-related hospitalization. Mild asthmatics treated only with pro re nata short-acting β_2 -agonists, less than 2 doses per week can be enrolled.
3. History of chronic sinusitis, defined as a sinus symptoms lasting greater than 12 weeks that includes 2 or more major factors or 1 major factor and 2 minor factors. Major factors are defined as facial pain or pressure, nasal obstruction or blockage, nasal discharge or purulence or discolored postnasal discharge, purulence in nasal cavity, or impaired or loss of smell. Minor factors are defined as headache, fever, halitosis, fatigue, dental pain, cough, and ear pain, pressure, or fullness.
4. History of systemic disease affecting the immune system such as autoimmune diseases, immune complex disease, or immunodeficiency, where, in the opinion of the study physician, participation in the study would pose a risk or significant effect on the immune system.
5. Presence or history of drug hypersensitivity to fexofenadine and/or its excipients.
6. The use of any investigational drug within 30 days of the EEU procedures.
7. Treatment with any antihistamine within 5 days of screening and within the defined washout period. Subjects receiving build-up injections of pollen allergen immunotherapy are to be excluded, whereas those on stable maintenance dosing can be included.

8. Subjects receiving systemic immunosuppressive treatment should be excluded.
9. Subjects unable to stop the following forbidden treatments/nutriments prior to pollen challenge:
 - a. Antihistamines: within 3 days for first-generation antihistamines, within 2 days for second-generation antihistamines.
 - b. Intranasal or inhaled corticosteroids: 7 days.
 - c. Ocular, intranasal, or inhaled sodium cromoglycate: 14 days.
 - d. High doses of systemic corticosteroids: 30 days.
 - e. Leukotriene antagonists: 30 days.
 - f. Intranasal or systemic decongestants: 3 days.
 - g. Tricyclic antidepressants: 7 days.
 - h. Any citrus fruits (grapefruit, orange, etc.) or their juices, as well as all fruit juices: 5 days.
 - i. Aluminum-and-magnesium containing antacids: 7 days.

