6.3 Measures to Minimize Bias: Randomization and Blinding

6.3.1 Randomization

The subject randomization list will be supplied to the study site by the clinical research organization (CRO).

Day 1 to Day 3 (double-blind, placebo-controlled part):

All participants will be centrally assigned to randomized study drug at Visit 3 (Day 1) as per the randomization list. The study site staff will record the subject number allocated at the time of screening and wallet number in the electronic case report form (eCRF). After the individual study drug wallets are assigned, the dispensing staff can ensure their numbers are correct and the participant has not already been randomized. Individual study drug wallets (containing 3 tablets of either fexofenadine or placebo – 2 doses and 1 additional tablet in case of loss) will be dispensed to the participants as assigned. The participants will be instructed by the study staff, to consume 1 tablet of study drug, each on Day 2 and Day 3 at home. The participant will return the used study drug wallet (containing 1 remaining tablet) when they return to the study site on Day 4, before the pollen challenge. Returned study drug should not be re-dispensed.

Day 4 (open-label part, post pollen challenge):

The participants will be exposed to a 3-hour pollen challenge at Visit 4 (Day 4). The study site staff will provide a commercial pack of fexofenadine 180 mg to each participant and instruct the participants to consume only one tablet from the pack. At H3, post pollen challenge, each participant will take the study drug at exactly the same time in the EEU. This time point will be recorded by study staff. The commercial pack of fexofenadine 180 mg with remaining tablets will be returned to the study site staff by each participant before leaving the EEU after completing all assessments at H6.

Stratification

Participants will be randomized to study drug at Visit 2. Stratification of TNSS-3 ≤ 7 /TNSS-3 > 7 will be documented in the Statistical Analysis Plan (SAP).

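### The antihistamine ban in protocol 6.8.1 does not cover the home scoring period from H6 to H12 on Day 4, a small and easily closed gap that touches only secondary endpoints

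*Protocol*

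**What the plan says.** Protocol 6.8.1 holds two antihistamine rules. The list that applies before each challenge reads "Antihistamines: within 3 days for first-generation antihistamines, within 2 days for second-generation antihistamines". The list of drugs prohibited during the study has the entry "Any antihistamine (during the washout period"). Decongestants, intranasal corticosteroids, cromoglycate and leukotriene antagonists appear in that second list with no such time limit.

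The other relevant rules stop at the same point or earlier. Section 4.1.3 says "During the washout period of at least 15 days, any antiallergic therapy is forbidden". Exclusion criterion 7 in section 5.2 covers "Treatment with any antihistamine within 5 days of screening and within the defined washout period". Criterion 9 applies only before a challenge.

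For the time after the challenge, section 2.3.2 says of fexofenadine "which they can continue at home after the pollen challenge is over if they wish to". Section 6.3.1 has the open-label pack "with remaining tablets will be returned to the study site staff by each participant before leaving the EEU". Section 6.7 treats more than 180 mg of fexofenadine in 24 hours as an overdose. Section 6.8.2 allows the site to supply rescue medication, with cetirizine as its example. Section 6.8 requires every concomitant drug to be recorded, with start and end dates.

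Sections 1.3 and 4.1.6 schedule hourly symptom scores at home from H6 to H12. SAP 16.2.1 uses them in the H0-H12 AUCs of TNSS-3 and TOSS. Both AUCs are in the secondary family that SAP 7.5 tests by Hochberg's procedure once the primary endpoint is significant.

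**The concern.** The test drug is an antihistamine, yet among the anti-allergic classes in the during-study list only antihistamines have a ban that ends with washout. Participants go home at H6 after a pollen challenge and score themselves hourly for six hours. If they take their own antihistamine then, they will do so because of symptoms. If pre-treatment works, Arm B participants have more reason to take it, and the between-arm difference in the H0-H12 AUCs shrinks.

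Site-supplied rescue is a deliberate part of the design and is recorded as such. A participant's own supply is neither barred nor, in the readable text, classed as rescue. The SAP marks intercurrent events as not applicable (7.4 and 16.2.2), so no visible rule says how scores after such use are treated.

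**Working it through.** The plan gives no figure on this point, so there is none to reproduce. The check sets the rules against the calendar and then sizes the exposed window.

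**1. Which intervals are covered.** On the nominal calendar V4 is Day 4. The 2-day bar (second generation) covers Days 2 and 3. The 3-day bar (first generation) covers Days 1 to 3. The remaining rule ends with washout. After the V4 challenge no antihistamine rule applies, so H6 to H12 at home is open.

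**2. Day 1.** Only second-generation drugs are open on Day 1, and how much of that day depends on where washout ends. Section 4.2 places washout "between the skin prick test to identify eligible participants and randomization (D1"), and the schedule of activities agrees, so Day 1 up to V3 is covered. Section 4.1 can be read the other way: "Randomization may occur within a week after completion of the washout period". On the first reading only the hours after V3 remain. A dose then cannot change the Day 1 score and could at most reach the Day 2 pre-dose score. Study drug starts on Day 2, so Day 1 use has no treatment-related reason to differ between arms.

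**3. Weight of the home scores in the H0-H12 AUC** (linear trapezoid, SAP 16.1.1 and 16.2.1).
- V4 scores: 13 (H0 to H3, every 15 minutes) + 6 (to H6, every 30 minutes) + 6 (H7 to H12, hourly) = 25. The H6 score is taken in the unit.
- Weights: H7 to H11 at 1 h each = 5 h; H12 = 0.5 h; total 5.5 h.
- Share: 5.5 / 12 = 45.8%. The share of the H0-H6 primary AUC is 0%.

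**4. Size of the shift in the TNSS-3 AUC.** Shift = (between-arm difference in the proportion using) × (points by which each home score falls) × 5.5 h. The first two inputs are assumptions, because the documents give neither. The SD of 15 is the planning value in protocol 9.5, which comes from an H2-H12 AUC.

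| Difference in use | Fall per score | Shift (score-hours) | Shift / 15 |
|---|---|---|---|
| 2 points of percentage | 1 | 0.02 × 1 × 5.5 = 0.11 | 0.007 |
| 5 points of percentage | 2 | 0.05 × 2 × 5.5 = 0.55 | 0.037 |
| 10 points of percentage | 3 | 0.10 × 3 × 5.5 = 1.65 | 0.11 |

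**5. Is the last row plausible?** The planning AUC over the 10 hours H2 to H12 is 18.53 on fexofenadine and 26.34 on placebo, so the mean TNSS-3 is 18.53 / 10 = 1.85 and 26.34 / 10 = 2.63. A 3-point fall exceeds both means, and every participant here has fexofenadine at H3. Capping the fall at 1.85 gives 0.10 × 1.85 × 5.5 = 1.02 score-hours, and 1.02 / 15 = 0.07 SD. More symptomatic users could fall further than the average, but the last row is an extreme.

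**6. Dose arithmetic.** H6 to H12 lies 3 to 9 hours after the H3 dose. A further 180 mg tablet in that window makes 360 mg within 24 hours, above the section 6.7 limit.

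**The case against.** Much of the case on the other side stands.

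- **Some qualifier was needed.** An unqualified ban during the study would have caught study drug and rescue. That is true, and it justifies an exemption for those uses. It does not explain silence on a participant's own supply.
- **Other controls exist.** Section 6.8 lets the investigator and medical monitor consider any concomitant drug case by case, and use must be recorded. These make use visible but do not bar it.
- **Reasons for use are limited.** The trial runs outside ragweed season, and criterion 12 excludes significant perennial allergy that cannot be avoided. This weakens the Day 1 part almost entirely. It weakens H6 to H12 less, since that window follows a challenge.
- **The remedy is partial.** Rescue cetirizine stays in the same window and works in the same direction. This stands and limits the gain.

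A reader might also infer three stronger things that the documents do not support. The first is that section 2.3.2 invites a second fexofenadine tablet on Day 4. It gives no time or dose and can be read as resuming on Day 5, which fits the pack return and the 24-hour limit; the fault is that it does not say so. The second is that a Day 4 intake cannot be ordered against the home scores. Section 6.8 asks only for dates, but section 4.1.6 collects concomitant and rescue medication in the same e-diary as the scores, and the forms are not in the documents. The third is that nothing at all handles such use. The exploratory sections of the SAP, which may cover rescue, are redacted.

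**Conclusion.** The gap is real and minor. By the stated rules, a participant's own antihistamine is not barred from H6 to H12 on Day 4, and the scores taken then carry 45.8% of the weight in two formally tested secondary AUCs.

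The likely effect on the TNSS-3 H0-H12 difference is small: from 0.007 SD to under about 0.1 SD, on assumed differences in use of 2 to 10 percentage points and a fall that does not much exceed the planning mean score. The documents give no planning SD for TOSS, so no size is offered there. If Arm B uses more, the shift is towards no difference. It would therefore cost sensitivity and would not create a false positive.

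It would be wrong to read this as a threat to the primary result: H0 to H6 is scored in the unit, and the window in question has no weight in that AUC. The Day 1 gap is negligible.

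**What to change.** 1. In 6.8.1, replace the washout qualifier with a bar on any non-study antihistamine from the start of washout through the H12 score on Day 4. Exempt assigned study drug, the H3 dose and site-supplied rescue. This also closes Day 1, and section 4.1.3 already refers to 6.8, so it can stand.
2. In 2.3.2, state that fexofenadine may be resumed no sooner than 24 hours after the H3 dose, in line with the 180 mg per 24 hours limit in 6.7.
3. Require the clock time of any antihistamine or rescue taken on Day 4, if the e-diary does not already capture it.

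The cost is wording in two sections and at most one data field, with no added analysis. The downside is a few more protocol deviations. Permitted rescue antihistamine still remains in the H0-H12 AUCs.

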6.8.2 Rescue Medicine

Rescue medication (eg, cetirizine) will be provided to the participants at the discretion of the Investigator, as per clinical judgment in order to manage symptoms. Rescue medication will not be blinded. Separate, open-label packets of marketed drug will be purchased locally by the study site and given to the participants by the study site staff/Investigator, as and when needed.

7.0 DISCONTINUATION OF STUDY DRUG AND PARTICIPANT DISCONTINUATION/WITHDRAWAL

Discontinuation of specific study sites or of the study as a whole are detailed in [Section 10.1.11](#).

7.1 Discontinuation of Study Drug

It may be necessary for a participant to permanently discontinue study drug if any of the following criteria are met:

- Important Protocol violation
- Withdrawal of consent by a participant
- Participant is lost to follow-up
- Inadvertent enrollment of a participant
- Pregnancy – see [Section 8.3.5](#)
- Termination of the study by the Sponsor

If study drug is permanently discontinued, the participant will remain in the study until EOS on D5. See [Section 1.3](#) for data to be collected at the time of discontinuation of study drug and follow-up and for any further evaluations that need to be completed.

If a participant who does not meet enrollment criteria is inadvertently enrolled, that participant must be discontinued from study drug and the Sponsor, or Sponsor designee, must be contacted. An exception may be granted in rare circumstances for which there is a compelling safety reason to allow the participant to continue. In these rare cases, the Investigator must obtain documented approval from the Sponsor, or Sponsor designee, to allow the participant to continue in the study.

Participants who discontinue study drug will not be replaced.

